1.2.8 Early closure by the DSMB and revision to study conduct

Enrollment into the DoxyPEP study was stopped early on 5/13/2022, as a prespecified interim data analysis demonstrated that the study had crossed pre-specified effectiveness thresholds. At the time of interimr review of 554 participants enrolled, a single dose of 200 mg doxycycline taken after condomless sex significantly reduced the acquisition of gonorrhea, chlamydia and syphilis in men who have sex with men (MSM) and transgender women (TGW). The effectiveness of doxycycline PEP was observed and statistically significant both in the cohort of participants living with HIV and the cohort of participants without HIV who were taking PrEP. The strategy of doxyPEP was safe and well-tolerated, with no doxycycline-associated Grade 2 or higher adverse events and no doxycycline-associated serious adverse events.

Enrolled participants will be notified of the study early closure and of the finding of doxycycline effectiveness to reduce STIs. They will also be informed that the impact of doxycycline PEP on antimicrobial resistance in STIs, *S. aureus*, commensal *Neisseria* and the gut microbiome is still under investigation. This protocol modification amends the study to offer doxycycline to enrolled participants assigned to the standard of care arm for the remainder of their 12 month participation. Participants who roll over from the control arm into the active doxycycline PEP arm will undergo the same evaluations as specified for the active arm (e.g., safety labs) per the schedule of events and will continue with quarterly study visits through month 12. At the time of roll over onto active doxycycline PEP, a rectal swab to establish the microbiome baseline prior to starting doxycycline will be collected. Participants who decline to roll over into the active doxycycline arm will have the option of remaining on study through month 12 following the standard of care arm schedule of events. All

participants will review and sign a revised informed consent at the time of their next study visit to consent to continuation in the study and to receive doxycycline, for those in control arm who chose to roll over to active doxyPEP.

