7 ADVERSE EVENTS (AE) AND STUDY MONITORING

7.1 Adverse Event Collection Requirements

All AEs must be recorded on eCRFs if any of the following criteria have been met:

- All grade 2 and higher hematologic and hepatic laboratory abnormalities that are attributed to doxycycline in the opinion of the site investigator
- All AEs meeting SAE definition
- All grade 3 and 4 adverse events judged to be associated with doxycycline (possibly, probably, or definitely related)

Serious Adverse Events (SAEs)

An SAE is defined as any untoward medical occurrence that:

- Results in death
- Is life-threatening
- Requires inpatient hospitalization or prolongation of existing hospitalization
- Results in persistent or significant disability/incapacity
- Is an important medical event that may not be immediately life-threatening or result in death or

hospitalization but may jeopardize the patient or may require intervention to prevent one of the other outcomes listed in the definition above)

All AEs that are recorded must have their severity graded. To grade AEs, sites should refer to the Division of AIDS Table for Grading the Severity of Adult and Pediatric Adverse Events (DAIDS AE Grading Table), corrected Version 2.1, July 2017, which can be found on the DAIDS RSC website at https://rsc.tech-res.com/docs/default-source/safety/division-of-aids-(daids)-table-for-grading-the-severity-of-adult-and-pediatric-adverse-events-corrected-v-2-1.pdf

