2.2.2.2. Safety, tolerability and acceptability of doxycycline PEP

- Safety: All grade 2 and higher hematologic and hepatic laboratory abnormalities, all grade 3 and 4 adverse events judged to be associated with doxycycline (possibly, probably, or definitely related), and all SAEs.
- Tolerability: in person quarterly assessments of discontinuations of doxycycline, discontinuation of PEP, symptom assessment, and self-reported side effects questionnaire at 6 and 12 months by CASI (computer assisted self-interview),

In person assessment by research staff at scheduled visits to include:

- All permanent doxycycline discontinuation and reasons for discontinuation;
- For all temporary doxycycline interruptions ≥ 7 days, reason for interruption; and
- Side effects:
 - o presence/absence of the following symptoms and if present, whether attributed to doxycycline (if taking) by a) participant and b) investigator: rash, sunburn, headache, change in vision, pain with swallowing, diarrhea, nausea, vomiting, abdominal pain, or other.

CASI questions related to tolerability

- At least once in the past 3 months, I did not take doxycycline within 3 days after sex because I wanted to avoid side effects. (Reported using 5-point Likert scale)
- Were there any other reasons that you did not take doxycycline within 3 days after sex? Yes/No (Y/N) and open-ended response if yes is selected.
- In the past 3 months, do you feel that taking doxycycline affected your sexual experience? (Reported using 3-point scale: negative, neutral, positive effect).

• Acceptability: self-reported acceptability questionnaire by CASI for all doxycycline PEP recipients administered at month 6 and 12.

Answer to the following questions, reported using a 5-point Likert scale, unless otherwise indicated

- Doxycycline is easy to take.
- I'm worried that taking doxycycline will cause antibiotic drug resistance. (reverse coded)
- I'm worried that doxycycline will hurt my body. (reverse coded)
- Taking doxycycline PEP will reduce my condom use. (reverse coded)
- Doxycycline has other good effects for me.
- Taking doxycycline PEP has helped me take my PrEP or ART more regularly.
- A sexual partner has expressed negative feelings about me taking doxycycline. (reverse coded)
- A sexual partner has expressed positive feelings about me taking doxycycline
- Taking doxycycline only when needed after sex and not every day is... (5-point scale from very unacceptable to very acceptable)

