3.5. Clinical Assessments

Safety assessments are limited to the following:

- All grade 2 and higher hematologic and hepatic laboratory abnormalities that are attributed to doxycycline in the opinion of the site investigator
- All AEs meeting SAE definition
- All grade 3 and 4 adverse events judged to be associated with doxycycline (possibly, probably or definitely related)

In this open label trial, for those randomized to receive doxycycline PEP, all AEs and SAEs have attribution recorded as doxycycline-related or not doxycycline-related, in the judgment of the site investigator.

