8.1. Adverse Events and Deaths

8.1.1. AE Definitions

Only the following AEs are recorded on eCRFs:

- All grade 2 and higher hematologic and hepatic laboratory abnormalities.
- All SAEs.
- In those randomized to doxycycline PEP arm, all grade 3 and 4 AEs with attribution to doxycycline in the opinion of the site investigator.

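### Protocol 1.2.8 reports no doxycycline-associated Grade 2 or higher adverse events, but non-serious Grade 2 clinical events were not required to be recorded, so the data cannot establish that zero

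*Protocol*

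**What the plan says.** The conclusion is in Protocol 1.2.8, which reports the interim review of 554 participants. It calls the strategy safe and well tolerated, "with no doxycycline-associated Grade 2 or higher adverse events and no doxycycline-associated serious adverse events".

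Protocol 7.1 gives three routes onto the adverse event form:

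- The laboratory route reaches down to Grade 2: "All grade 2 and higher hematologic and hepatic laboratory abnormalities that are attributed to doxycycline in the opinion of the site investigator".
- The second route takes in every serious event, whatever its grade or type.
- The third route covers whatever is left, including non-serious clinical events, and starts one grade higher: "All grade 3 and 4 adverse events judged to be associated with doxycycline (possibly, probably, or definitely related").

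Severity grading is tied to that list: "All AEs that are recorded must have their severity graded".

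The SAP repeats the three categories in exclusive terms. Section 3.5 opens with "Safety assessments are limited to the following", and section 8.1.1 with "Only the following AEs are recorded on eCRFs". The two differ on one detail: Protocol 7.1 and SAP 3.5 limit the laboratory category to abnormalities attributed to doxycycline, while SAP 2.2.2.2 and 8.1.1 list all of them.

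Milder clinical effects are followed separately, as tolerability. SAP 2.2.2.2 records "presence/absence of the following symptoms and if present, whether attributed to doxycycline (if taking) by a) participant and b) investigator", together with the reasons for permanent discontinuation and for interruptions of at least seven days.

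**The concern.** The sentence in 1.2.8 covers every kind of adverse event from Grade 2 upward. The recording rules reach down to Grade 2 only for blood counts and liver tests. Protocol 1.2.1 describes hematologic and hepatic toxicity as rare (under 1%), whereas Protocol 5.2 lists the most common side effects as gastrointestinal, esophageal and skin reactions, all of them clinical. So the Grade 2 threshold applies where few events are expected and not where most are.

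At stake is how the safety evidence is described. SAP 4.1 says that a decision to stop for efficacy has to be weighed against the need for evidence on harm from side effects. Section 1.2.8 is where the protocol summarises that evidence, and the same section offers doxycycline to the control arm. It also says that the continued follow-up will inform guidelines. A zero that partly reflects what sites were not asked to record should not be carried into later reports as an observed absence.

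**Working it through.** **Step 1. Follow a non-serious, doxycycline-related Grade 2 clinical event (for example, nausea) through each route.**

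| Route | What is recorded | Would the event appear with its grade? |
|---|---|---|
| Protocol 7.1, SAP 3.5 and 8.1.1: laboratory | Grade 2 or higher, hematologic or hepatic | No, it is not a laboratory finding |
| Same sections: SAEs | Any grade, if serious | No, it is not serious |
| Same sections: related events | Grade 3 and 4 | No, it is below the threshold |
| Protocol 10.1.2, safety outcome | Attributed Grade 3 and 4 events | No |
| SAP 8.1.2, planned table from Grade 2 | Hematologic and hepatic events | No |
| Protocol 6.3.4, SAP 2.2.2.2: checklist | Presence and attribution | The symptom may; no grade is specified |
| Protocol 8.1: Grade 1 or 2 toxicity | Notice to the protocol team if the participant chooses to stop | Only if treatment stops; recording the grade is not required |
| Protocol 9.1, SAP 2.2.2.2: stopping and interruption | Reason | The reason may; no grade is specified |

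No listed route requires such an event to be recorded together with a grade.

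**Step 2. Split the claim in 1.2.8 into its components.**

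- Related Grade 2 or higher hematologic or hepatic laboratory abnormalities: within the rules.
- Related Grade 3 or 4 events: within the rules.
- Related SAEs: within the rules.
- Related, non-serious Grade 2 clinical events: outside the rules.

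Only the last component lacks support, but the unrestricted wording needs all four.

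**Step 3. What a zero is worth in each case.** The documents give no figure to reproduce here, so this is an illustration. The size of the doxycycline arm at the interim is not stated. Assuming 2:1 allocation, n = 554 × 2/3 ≈ 369, with 300 to 400 as a range.

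For a category that is collected, zero events give a one-sided 95% upper bound u from (1 − u)^n = 0.05, that is u = 1 − 0.05^(1/n):

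- n = 300: 0.99%
- n = 369: 0.81%
- n = 400: 0.75%

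Put the other way, with n = 369 the chance of seeing no events in a collected category is (1 − p)^369. For assumed true rates p of 1%, 2% and 5% this is about 0.025, 0.0006 and 6 × 10⁻⁹. For a category that sites do not record, the chance of zero is 1 at every p, so zero sets no bound.

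**The case against.** The strongest reply is that the rules state what must be recorded, which is a minimum. Protocol 7.3.1 has the team review individual safety data frequently, and Protocol 8.1 presupposes that sites grade related toxicity at Grades 1 and 2. The exclusive wording is in a SAP written against protocol version 5.0, while the current protocol is version 9.0. The interim report, case report forms and procedures manual are not among the documents. This stands as a limit: a reader might infer that no Grade 2 clinical event could have been in the interim data, and the documents do not show that. They show only that such events were not required and that no grade is specified for the other sources.

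Two further points stand. Serious Grade 2 clinical events are recorded, so it would be wrong to say that the trial records none. And tolerability is a separate outcome in Protocol 10.1.2, measured by a questionnaire in both arms and by discontinuations with reasons. The description of the strategy as well tolerated can rest on those data, and nothing in the documents contradicts it.

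It is also fair that limited monitoring was a reasoned choice (Protocol 1.2.1), that 1.2.8 attributes the early closure to effectiveness thresholds, and that no planned analysis depends on the sentence. None of this supports the unrestricted zero. A minimum rule does not show that events below it were looked for, graded and found absent.

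**Conclusion.** The statement in Protocol 1.2.8 is broader than the collection rules can support. Three of its four components fall within what was required; the absence of related, non-serious Grade 2 clinical events does not. The matter is confined to the wording of a safety conclusion. It does not touch the efficacy results or the reason given for closing enrollment.

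The conclusion rests on the text of the rules and on the absence of a specified grade in the checklist, interruption and discontinuation data. It does not depend on the assumed 369. That figure serves only to show the contrast between an upper bound of about 0.81% and no bound at all, and it treats every participant as fully assessed, although follow-up was incomplete at the interim.

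A reader might be tempted to estimate how many Grade 2 events went unrecorded, using the gastrointestinal side effects (25% against 14%) and the 7% discontinuation that Protocol 1.2.1 cites from the prior trial. The documents do not support such a count. Those side effects are not broken down by grade, so any Grade 2 share would be invented. They accrued over 8.7 months, whereas follow-up at this interim was incomplete. Discontinuations for side effects are not missing data, because their reasons are recorded.

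**What to change.** Restate the safety sentence in Protocol 1.2.8, and any text that draws on it, along these lines: there was no doxycycline-related hematologic or hepatic laboratory abnormality of Grade 2 or higher, no related Grade 3 or 4 adverse event and no related SAE; non-serious Grade 2 clinical events were not required to be recorded as adverse events.

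Beside it, present the checklist symptoms attributed to doxycycline and the interruptions and discontinuations for side effects. These are already collected and are the proper basis for a statement on tolerability. SAP 8.1.3 and 8.4 already cover discontinuations. Section 8 of the SAP does not name a table for the attributed checklist symptoms, so one descriptive table should be added. In the same edit, reconcile whether the laboratory category means all Grade 2 or higher abnormalities or only those attributed to doxycycline.

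The cost is a reworded sentence and a table from existing data; the safety statement becomes somewhat less sweeping. Adding a DAIDS grade to attributed checklist symptoms at the remaining visits is optional. It would need a new data field, would not be comparable with earlier visits, and would not repair the interim statement.

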2 STUDY DESIGN

Design: The overarching goal is to assess the effectiveness of doxycycline PEP on incidence of STIs and tetracycline resistance among STIs and commensal bacteria to inform public health policy. Participants will be randomized 2:1 (see Schema), with two-thirds receiving doxycycline PEP and one-third receiving the standard of care control, to maximize data on safety, tolerability, adherence coverage of sexual acts, and resistance data in participants randomized to doxycycline PEP, without negatively impacting power to measure effectiveness. Participants will be counseled about the preliminary effectiveness data from IPERGAY, and the potential for AMR in STIs or other bacteria. Possibility of unreported doxycycline use in the control arm (contamination) will be monitored through retrospective batch testing of doxycycline metabolites in hair, to detect doxycycline use in the prior 3 months. ⁵⁹

The trial of doxycycline PEP will be powered to separately assess impact for MSM living with HIV and MSM on PrEP because of potential differences in safety, tolerability, adherence, sexual networks, sexual practices, background AMR, and ultimately, PEP effectiveness. Eligible participants randomized 2:1 to receive PEP will receive open-label doxycycline 200 mg to be taken ideally within 24 hours but no later than 72 hours after condomless sexual contact (oral or anal). 200 mg of doxycycline will be taken at most once per 24 hour period regardless of the number of sexual acts occurring during this time period. the rationale for 2:1 randomization is to maximize data on doxycycline PEP safety, tolerability, acceptability, and resistance, while providing sufficient power for the primary outcome of the effectiveness of doxycycline PEP. Sexual activity will be recorded for both arms of the study (doxycycline PEP and control condition) by the participant using a smartphone application that will be adapted for study use; this will enable comparable assessment of risk in the two arms. PEP pill-taking will also be measured by the app to enable assessment of coverage of sex acts by PEP. Sexual activity and adherence will also be assessed in person at quarterly visits. STI testing will be conducted quarterly from three anatomic sites (pharyngeal, rectal, and urinary) and blood obtained for syphilis testing, following CDC guidelines for serologic diagnosis of syphilis. Participants with a positive STI test will return for STI treatment and for swabs of the affected site for resistance testing; culture based for GC and molecular methods for CT and syphilis. Those with signs and symptoms suggestive of syphilis infection and those with a reactive syphilis serologic test that indicates a new syphilis infection will have swabs of any current active lesion (if present) as well as mucosal swabs from the oropharynx. Swabs from the anterior nares and oropharynx will be obtained at baseline, 6 and 12 months to evaluate tetracycline resistance in S. aureus among carriers and oropharyngeal swabs will be obtained at baseline and 12 months to evaluate tetracycline resistance in commensal Neisseria species.

Stool samples from 100 participants on the doxycycline PEP arm – 50 MSM and TGW living with HIV and 50 MSM and TGW on PrEP– will be collected at baseline, 6 and 12 months to evaluate effects of intermittent doxycycline on the gut resistome, using FLASH targeted metagenomic sequencing to evaluate for tetracycline and other resistance genes. Rectal swabs will be collected and archived in all participants at baseline, 6, and 12 months for future studies of the impact of doxycycline PEP on the enteric microbiome and resistome.

Study population: This study will enroll 780 participants living with HIV and HIV-negative persons taking PrEP. An approximately equal number of PLWH and HIV uninfected persons taking PrEP will be enrolled. An approximately equal number of participants in each of these cohorts (and in each study arm) will be enrolled in

San Francisco and Seattle.

Current or planned initiation of PrEP use is an eligibility criterion for enrollment, because this population of MSM and TGW has high rates of STIs and is typically seen quarterly for PrEP visits. However, participants may opt to stop PrEP use at any time during the study without affecting their involvement in the study. Any participants without HIV infection who subsequently seroconvert will be managed clinically by the study site according to local practice (appropriate counseling, clinical evaluation, and immediate linkage to clinical and psychosocial services). These participants will also be retained in the study unless they choose to discontinue study participation.

3 OBJECTIVES

3.1 Primary Objectives

- 3.1.1 Evaluate the effectiveness of doxycycline post-exposure prophylaxis (PEP) to reduce STI infections in two populations: a) MSM/TGW living with HIV and b) MSM/TGW taking HIV PrEP.
- 3.1.2 Investigate the impact of doxycycline PEP on development of culture-based tetracycline (TCN) resistance in *N. gonorrheae* and among nasopharyngeal carriers of *S. aureus*

3.2 Secondary Objectives

- 3.2.1 Assess the safety, tolerability, and acceptability of doxycycline PEP
- 3.2.2 Investigate the impact of doxycycline PEP on detection of culture and molecular markers of tetracycline (TCN) resistance in *C. trachomatis* (CT), and *T. pallidum* (syphilis- molecular markers only).
- 3.2.3 Measure the proportion of sex acts which are covered by doxycycline PEP
- 3.2.4 Evaluate the development of phenotypic TCN-resistance among oropharyngeal carriers of commensal *Neisseria* species
- 3.2.5 Assess the effect of doxycycline PEP on the gut resistome through measuring the abundance of tetracycline resistance genes in stool of a subset of 50 MSM living with HIV and 50 MSM/TGW on PrEP assigned to receive doxycycline PEP as well as rectal swabs from all participants, stored for future evaluation

3.3 Exploratory objectives

- 3.3.1 Evaluate the diversity of the gut microbiome and quantity and breadth of drug resistance genes in participants on doxycycline PEP and not on PEP
- 3.3.2 Assess the association between meningococcal vaccination and incident GC infection
- 3.3.3 Evaluate the incidence of urethritis without identified bacterial etiology and the proportion which is associated with MG in each arm
- 3.3.4 Assess the rate of detection of *Mycoplasma genitalium* (MG) in urine in each arm and the presence of tetracycline and other antimicrobial resistance in MG in each arm.
- 3.3.5 Evaluate association of doxycycline use with weight change over time
- 3.3.6 Evaluate whether doxycycline PEP is associated with PrEP persistence and HIV virologic suppression by comparison of arms and within the doxycycline PEP arm by adherence to doxycycline PEP.
- 3.3.7 Evaluate the incidence of lymphogranuloma venereum (LGV) in those diagnosed with rectal chlamydia in each arm

4 SELECTION AND ENROLLMENT OF PARTICIPANTS

4.1 Inclusion criteria

- 4.1.1 Willing and able to give written informed consent
- 4.1.2 Age > 18 years
- 4.1.3 Male sex at birth
- 4.1.4 Previously HIV-diagnosed
 - OR

HIV-seronegative at the time of last test within the past three months and a current prescription for PrEP (both daily or event-driven PrEP permitted) or plan to start PrEP within 30 days after the enrollment visit

- 4.1.5 Condomless anal or oral sexual contact with ≥ 1 male sex-at-birth partners in the past 12 months
- 4.1.6 Diagnosed with GC, CT or syphilis in the past 12 months.

Note: self report of STI is acceptable if documentation not available. If the participant reports an incident STI in the past year at the same clinic where the participant will be enrolled, this diagnosis should be confirmed by chart review prior to enrollment. If the diagnosis from this clinic cannot be confirmed, the participant should not be enrolled. If the STI was reported at a clinical site that is not the study site, and records cannot be obtained, self-report will suffice.

Note: Syphilis diagnosis within the last year refers to primary syphilis, secondary syphilis, and documented early latent syphilis (< 1 year since last syphilis diagnosis or negative test). Known late latent syphilis or latent syphilis of unknown duration would not qualify. Positive syphilis titers which represent serofast status and not active disease do not qualify as a syphilis diagnosis. Clinician judgement regarding qualifying syphilis diagnosis should be sought when the diagnosis of syphilis in the past year is not clear or if there is a question about serofast status vs. active infection.

